1 **Study protocol**

2 **Title**

3 **Applying telemedicine technologies in a novel model of organizing and implementing**  
4 **comprehensive cardiac rehabilitation in heart failure patients – TELEREH-HF.**

5 **Introduction**

6 Heart failure (HF) epidemic is an aggressively developing phenomenon, stimulated by developing  
7 civilization and generating worrying economic and social effects. The benefits of cardiac  
8 rehabilitation in HF patients are well established. Therefore current guidelines strongly recommend  
9 exercise training as an important component of HF management. Despite these facts, many HF  
10 patients do not undergo the programmes of cardiac rehabilitation. In Poland, cardiac rehabilitation  
11 availability is highly unsatisfactory (around 8%) and unacceptably varied (0.5-70%). With the  
12 existing organization and technical background, improving this situation seems impossible. Therefore  
13 we create the project: „To apply telemedicine technologies to implement a novel model of home-based  
14 comprehensive cardiac rehabilitation in HF patients”.

15 The project will enable early secondary prevention in the population of people with HF to be  
16 implemented. It will be achieved via:

- 17• Novel concept - "From Hospital To Home"
- 18• Novel technology - telemedicine
- 19• Novel method of comprehensive cardiac rehabilitation implementation

20

21 Hybrid comprehensive TELEREHabilitation in Heart Failure patients (TELEREH-HF) -  
22 a randomized, multi-center, prospective, open-label, parallel group controlled trial .

23 The TELEREH-HF trial is design to determine if a hybrid model of comprehensive telerehabilitation  
24 (TR) in HF patients influences days alive and out of hospital (DAOH) and prognosis when compared  
25 with usual care.

26

## 27 **Objectives**

28 **The primary** objective of the TELEREH-HF trial is to determine whether introducing a novel hybrid  
29 model of comprehensive TR in HF patients will significantly increase DAOH when compared with  
30 usual care.

31 **The secondary** objectives are to assess the effects of a hybrid comprehensive TR compared to usual  
32 care on all-cause and cardiovascular (CV) mortality and all-cause, CV and HF hospitalization.

33 **The tertiary analyses** will include: evaluation of the safety, effectiveness, quality of life (QoL),  
34 depression, anxiety, patients acceptance of and adherence to a hybrid comprehensive TR.

35

## 36 **Study design**

37 The TELEREH-HF study is a randomized, multicenter, prospective, open-label, parallel group  
38 controlled trial introducing a novel hybrid comprehensive TR in HF patients.

39 The study conduct is guided by good clinical practice, in accordance with the Declaration of  
40 Helsinki and the laws and regulations applicable in Poland.

41 The main investigator and Steering Committee designed the trial and wrote the study protocol. The  
42 study was approved by the local Ethics Committee. An independent Data Safety Monitoring Board  
43 will review patient data and a Clinical Endpoint Committee, blinded to treatment allocation, is  
44 appointed to adjudicate deaths and hospitalisations (**Table 1**). Each patient is obliged to provide  
45 written informed consent.

46

47 **Table 1.** The Principal Investigator, Members of the Steering Committee, The Data Safety  
48 Monitoring Board and The Clinical Endpoint Committee

Principal Investigator	[name]
Steering Committee	[name] (Warsaw, Poland; Chair), [name] Łódź, Poland), [name] PhD (Durham, NC, USA), [name] (Warsaw, Poland), [name] (Rochester, NY, USA)
Data Safety Monitoring Board	[name] PhD (Poznań, Poland; Chair), [name] (Warsaw, Poland), [name] (Warsaw, Poland)
Clinical Endpoint Committee	[name] (Warsaw, Poland; Chair), [name] (Warsaw, Poland), [name] (Warsaw, Poland)

49

50 The study is ongoing in 5 centers in Poland:

- 51
- Institute of Cardiology, Warsaw (Coordinating Center),
- 52
- Medical University of Gdansk,
- 53
- Silesian Center for Heart Diseases in Zabrze,
- 54
- Medical University of Lodz,
- 55
- Medical University of Warsaw.

56

57 **Study population, recruitment and randomization**

58 The TELEREH-HF study has a target enrollment of 850 clinically stable HF patients (New  
59 York Heart Association [NYHA] class I, II or III and left ventricular ejection fraction [LVEF]  $\leq$  40%)  
60 after a cardiovascular (CV) hospitalization incident within 6 months prior to randomization. The  
61 inclusion and exclusion criteria are shown in **Table 1**.

62 **Table 2. Inclusion and Exclusion Criteria**

63

Inclusion Criteria
Patients eligible for the trial have to meet the following criteria of randomization, i.e. patients need to: 
 
- be of either sex with any aetiology of left ventricular systolic heart failure as defined in the ESC guidelines
 
- have a LVEF <math>\leq</math> 40% on echocardiography
 
- belong to NYHA class I, II or III
 
- have had a hospitalization incident within 6 months prior to randomization
 
- be stable clinically (a patient does not need intravenous medication or has not had therapy modified for at least 7 days)
 
- have no contraindications to undergo cardiopulmonary exercise test
 
- be able to exercise using the new model of hybrid telerehabilitation
 

Exclusion Criteria

None of the following conditions may exist at randomisation:
 
 
- NYHA class IV
 
- unstable angina
 
- unstable clinical status
 
- a history of acute coronary syndrome within the last forty days in patients with LVEF <math>\leq</math> 35%
 
- percutaneous angioplasty within the last 2 weeks
 
- coronary artery bypass grafting within the last 3 months
 
- implantation/initiation of CRT-P or CRT-D or ICD or PM within the last six weeks
 
- lack of ICD, CRT-P or CRT-D or PM therapy despite the indications for implantation according to ESC guidelines
 
- intracardiac thrombus
 
- rest heart rate <math>></math>90/min
 
- tachypnoe <math>></math>20 breaths per minute
 
- symptomatic and/or exercise-induced cardiac arrhythmia or conduction disturbances
 
- acute myocarditis and/or pericarditis
 
- valvular or congenital heart disease requiring surgical treatment
 
- hypertrophic cardiomyopathy
 
- severe pulmonary disease
 
- uncontrolled hypertension
 
- anemia (hemoglobin <math><</math>11.0 g/dL)
 
- physical disability related to severe musculoskeletal or neurological problems
 
- recent embolism
 
- thrombophlebitis
 
- acute or chronic inflammatory disease
 
- acute or chronic decompensated non-cardiac diseases (thyreotoxicosis, uncontrolled diabetes)
 
- active malignant neoplastic diseases with survival prognosis below 2 – 5 years
 
- orthotropic heart transplant in anamnesis
 
- presence of an implanted left ventricular assist device or biventricular assist device
 
- aortic aneurysm
 
- severe psychiatric disorder
 
- patient's refusal to participate
 

64 ESC - European Society of Cardiology, LVEF - left ventricular ejection fraction, NYHA - New York Heart  
65 Association, CRT-P - cardiac resynchronization therapy, CRT-D - cardiac resynchronization therapy and  
66 implantable cardioverter-defibrillator, ICD - implantable cardioverter-defibrillator, PM - pacemaker  
67

[figure not shown]
68 Eligible patients will be randomized in 1:1 ratio to either hybrid TR + usual care (TR group)  
69 or to usual care only control group (CG) via a secure web-based randomization system – Research  
70 Electronic Data Capture (REDCap) housed in the Coordinating Center. All sites will use the same  
71 allocation process to ensure uniform randomization.

72 The study schedule is shown in **Figure 1**.

73  
74  
75  
76  
77  
78

**Figure 1.** The study schedule and follow-up.

79  
80  
81  
82  
83  
84  
85  
86  
87  
88  
89

112  
113  
114  
115  
116

\* All patients whose 24-month follow up is not later than 31/03/2019 (in accordance with the regulations of the National Center for Research and Development).

### 117 **Intervention in Telerehabilitation Group**

118 The TR group patients will undergo a 9-week hybrid comprehensive TR program consisting of  
119 two stages: an initial stage (1-week) conducted at hospital and a basic stage 8-week home-based TR

120 five times weekly. The goals of the initial stage are: a baseline clinical examination, optimization of  
121 treatment, education, individual planning of exercise training and performing five monitored  
122 educational training sessions. The basic stage, which is conducted at home consisted of two parts, is  
123 performed prior to each training session: the first part - the training consent procedure is required for a  
124 patient to access each training session, and the second part - the training session.

125

## 126 **Telemonitoring**

### 127 Remote monitoring during rehabilitation and training consent procedure.

128 Telerehabilitation is carried out by a medical team and advanced monitoring systems are used.  
129 A TR medical team is composed of: physicians, physiotherapists, nurses and a psychologist. The  
130 monitoring system includes: (1) a special remote device for tele-ECG-monitored and supervised  
131 exercise training - TR set (manufactured by Pro Plus Company, Poland), which consists of: EHO mini  
132 device, blood pressure measuring and weighing machine, (2) data transmission set via a mobile phone,  
133 (3) a monitoring centre capable of receiving and storing patients' medical data (specialized hardware  
134 and software are necessary).

135 **Figure 2.** Telerehabilitation set — a weighing machine, the EHO mini device, a manometer.  
136

137

138

139           The TR group patients will receive a TR set and mobile phone. The EHO mini device is able  
140 to record ECG data from three pre-cordial leads and transmit them via a mobile phone network to the  
141 monitoring center. An EHO mini device has training sessions preprogrammed individually for each  
142 patient (defined exercise duration, breaks, timing of ECG recording). The moments of automatic ECG  
143 registration are preset and coordinated with the exercise training. The planned training sessions are  
144 executed with the device indicating what needed to be done with sound and light signals. There are  
145 sound signals in the form of bleeps and light signals from color emitting diodes. Bleeps and green  
146 diode blinking meant that the patient has to perform exercise. Another set of bleeps and red diode  
147 blinking meant “stop exercise”. The timing of automatic ECG recordings correspond to peak exercise.

148           An EHO mini device has a tele-event-Holter ECG feature as well. It enables a patient,  
149 whenever a worrying symptom occurs, to register and immediately send the ECG recording via mobile  
150 phone network to the telemonitoring center.

151           Before beginning a training session, patients will use the mobile phone to answer a series of  
152 questions regarding their present condition, including fatigue, dyspnea, blood pressure, body mass,  
153 and medication taken. Patients then will transmit resting ECG data to the monitoring center. Before  
154 giving permission to start the training session, the medical staff also will analyze data from the remote  
155 monitoring of CIEDs. If no contraindications to training are identified, patients will be given  
156 permission to start the training session. The system is used to monitor and control the training in  
157 any place where the patient will decide to exercise. If the training session is completed uneventfully,  
158 the patient will transmit the ECG recording via the mobile phone network to the monitoring center  
159 immediately after the end of every training session. The ECG recordings will be analyzed at the  
160 monitoring center, and the safety, efficacy, and accuracy of a tailored patient’s rehabilitation program  
161 will be assessed. Using the data on heart rate (HR) during exercise and the patient’s subjective  
162 evaluation of the perceived exertion according to Borg scale, consultants will be able to adjust the  
163 training workload appropriately or, if necessary, to discontinue the session. Telephone contact is also  
164 use for psychological support.

165

166 Remote monitoring of cardiac implantable electronic devices (CIEDs)

167           Additionally, TRG patients with CIEDs (if technical requirements were complied with) will  
168 receive the transmitter (Biotronik - CardioMessenger; Medtronic transmitter [Home Monitor] of the  
169 CareLink™ network; St-Jude – Merlin@home™ wireless transmitter) which allows the automatic  
170 transmission of data from the implant to a web-based monitoring platform (Biotronik – Home  
171 Monitoring Service Center, Medtronic – CareLink-Network , St-Jude – Merlin.net™Patient Care  
172 Network). Remote monitoring will rely on data acquired automatically on a daily basis by the device,  
173 with unscheduled transmission of any predefined alerts to the medical staff in each center. These alerts  
174 involved device integrity [e.g. battery status- the battery depletion indicators: end of service (EOS), the  
175 elective replacement indicator (ERI) lead impedance], programming issues [e.g. disabling of  
176 ventricular fibrillation (VF) therapy, antitachycardia pacing (ATP) therapy, insufficient safety margins  
177 for sensing or capture], and medical data [e.g. arrhythmias – supraventricular tachycardia (SVT)/atrial  
178 fibrillation (AF)/atrial flutter (AFI), ventricular tachycardia (VT)/VF, indication of lung fluid  
179 accumulation].

180           In addition, each patient with CIEDs and a remote monitoring device will have scheduled  
181 standard follow-up visits in order to evaluate the device functioning [after four weeks from the  
182 beginning of hybrid TR in TRG and usual care in CG and immediately after the intervention (after 9  
183 weeks) in the TG and the observation period in CG]. The following parameters will be evaluated:  
184 mean heart rates, patient activity, supraventricular (SVT, AF/AFI) and ventricular [non-sustained VT  
185 (nsVT), VT/VF] arrhythmia, impedance, percentage of resynchronization stimulation, intracardiac  
186 electrogram (IEGM).

187

188 Exercise training

189           Cardiac rehabilitation is planned according to the published guidelines for HF patients. In  
190 order to ensure patients safety, the following recommendations will be taken into account: (1) special  
191 attention is paid to appropriate patient risk stratification before cardiac rehabilitation; (2)  
192 contraindications to exercise training are never overlooked (**Table 3**); (3) in patients with an

193 implantable cardioverter-defibrillator (ICD), maximal training HR is set at 20 b.p.m. lower than the  
 194 ICD discharge threshold; and (4) in patients with a pacemaker, cardiac resynchronization therapy  
 195 (CRT-P), cardiac resynchronization therapy and implantable cardioverter-defibrillator (CRT-D), the  
 196 rate-response function is switched on, enabling HR adjustment to the physical effort which facilitated  
 197 reaching the desired training HR.

198 **Table 3. Contraindications to exercise training**  
 199

Acute worsening of exercise tolerance, dyspnoea or chest pain Increase of 1.8 kg or more in body mass over the previous 1–3 days Supine resting heart rate > 90 beat per minute New-onset cardiac arrhythmias: atrial fibrillation/atrial flutter/supraventricular tachycardia, complex ventricular arrhythmia at rest or appearing with exertion New-onset advanced atrioventricular block New-onset of significant ischaemia during low-intensity exercise Decrease in systolic blood pressure with exercise Uncontrolled hypertension, resting blood pressure >140/90 mmHg Recent embolism Recent thrombophlebitis Acute systemic illness New-onset uncontrolled endocrine and metabolic disorders
---

200

201 Exercise trainings will be planned individually for each patient during hospitalization.

202 The telerehabilitation program encompasses three training modalities: endurance aerobic Nordic  
 203 walking training, respiratory muscle training and light resistance and strength exercises. The details  
 204 are presented in **Table 4** and **Table 5**.

205 **Table 4. Exercise training model**  
 206  
 207

Type of exercise training	Exercise prescription
Aerobic endurance training	Devices: Nordic walking poles Training session consists of: 1. Warm-up: breathing and light resistance exercises using poles for Nordic walking; duration 5–10 min 2. Nordic walking training Intensity: 40-70% of heart rate reserve, perceived exertion level—score of 11-12 on the Borg scale Duration: start at 10 min/session/day a 15 min/session/day b 20 min/session/day c gradually increased to 30–45 min/session/day d 3. Cool down: relaxation, breathing exercise; duration 5 min Frequency: 1 session/day

Respiratory muscle training	Devices: Train Air software - during the initial stage at the hospital Threshold Inspiratory Muscle Trainer - during the basic stage at home Intensity: start at 30% of the maximal inspiratory mouth pressure ( $PI_{max}$ ) and readjusted to a maximum of 60% (if possible) Duration: minimum 5-10 minutes/day maximum 20-30 minutes/day; Frequency: 3-5 times/ throughout the day
Resistance and strength training	Devices: Thera Band - yellow color Intensity: 5-10 repetitions of each of the seven exercises (see Appendix 2) Duration: gradually increased 5-10-15 minutes/day Frequency: 1 session/ day

208  
209  
210  
211  
212

Duration of aerobic endurance training depended on the functional capacity in baseline cardiopulmonary exercise test:

abaseline peak  $VO_2$  below 10 mL/kg/min.

bbaseline peak  $VO_2$ : 10–18 mL/kg/min.

cbaseline peak  $VO_2$  over 18 mL/kg/min.

213

214 **Table 5. Resistance and strength exercise using Thera band**

215

[figure not shown]

Upper limbs

Exercise 1. Position: sitting, the center of the band under the right / left foot. We keep the ends of the tape in the right / left hand. Flexing the right / left elbow.


Exercise 2. Position: sitting, the center of the band under the right / left foot. We keep the ends of the band in the right / left hand. Raise the right / left upper limb to the level of the shoulder.

**Exercise 3.** Position: sitting, band placed on the back. We grab the ends of the band. Upper limbs flex at the elbows at the chest level, hands keep the tape slightly taut. We stretch the tape as far forward as possible, trying to keep the movement horizontally at chest level.

[figure not shown]

**Exercise 4.** Position: standing in the middle of the band. The band crossed in front of the body. Abduction of the arms and returning to the starting position.

[figure not shown]

## Lower limbs

[figure not shown]
**Exercise 5.** Position: sitting, the center of the band under the foot, the ankle joint extended (dorsiflexion). The ends of the band are held in the hands at the level of the knee joint. The band tight. Plantar flexion of the ankle.

**Exercise 6.** Position: sitting, the hip and knee joint bent. Wrap the band wrapped around the foot with both hands. Hands are placed on the chest. Extension in the hip and knee joint.

**Exercise 7.** Position: Standing in a light stride, place the widely spread band under the foot of the supporting leg and attach it at the height of the ankle joint of the other limb. Abduction of the lower limb.

216

217           The chosen workload during Nordic walking is supposed to reflect individual effort tolerance  
218 with regard to: (1) perceived exertion according to the Borg scale and (2) the training HR range  
219 established individually for each patient based on cardiopulmonary exercise test (CPET) perform  
220 before the start of the TR program. In line with the recommendations, the assumption is that patients  
221 are not to exceed perceived moderate exertion during exercise training (i.e. a score of 11-12 on the  
222 Borg scale). The training HR is calculated using the method known as HR reserve. This method uses a  
223 percentage of the difference between the maximum HR and the resting HR rate, and adds this value to  
224 the resting HR. The target training HR is 40–70% of the HR reserve. Patients train five times a week.

225

#### 226 Education

227           Education program is designed and run by the TR team. Patients will be taught how to self-  
228 evaluate, how to measure HR, blood pressure, body mass, how to performed all modalities of exercise  
229 training, how to evaluate the level of perceived exertion according to the Borg scale and how to  
230 operate a TR set. Education will also encompass nutritional counselling, lipid management, smoking  
231 cessation, vocational and psychosocial support.

232

233 **Control Group**

234 Patients randomized to the CG will undergo baseline clinical examinations during a 3-day  
235 hospitalisation and then will be under observation until the end of the 9th week and will receive usual  
236 care appropriate for their clinical status and standardized within a particular center (some of them can  
237 participate in a rehabilitation program and some of them has remote monitoring of CIEDs). After the  
238 9th week patients will undergo final assessments during a 3-day hospitalization.

239 All patients, regardless of the treatment group, will receive recommendations for suitable  
240 lifestyle changes and self-management according to guidelines.

241

242 **Clinical examinations**

243 All 850 patients will undergo the following assessments at entry (during 5 days of  
244 hospitalization-TRG, and 3 days of hospitalisation-CG) and after completing the 9-week program  
245 (during 3 days hospitalisations – both groups): clinical examination with symptom evaluation (NYHA  
246 class), blood testing [blood count, serum creatinine, electrolytes (sodium, potassium), glycaemia, N-  
247 terminal pro B-type natriuretic peptide (NT-proBNP), aspartate aminotransferase, alanine  
248 aminotransferase, thyroid stimulating hormone (TSH), international normalized ratio (INR),  
249 urinalysis], ECG, two-dimensional echocardiography, six-minute walk test (6-MWT), CPET, 24 hours  
250 holter ECG monitoring, evaluation of CIEDs proper functioning, and psychological assessment: the  
251 QoL based on SF-36 Survey; the depression based on Beck inventory; the anxiety based on STAY.  
252 Additionally, after 9 weeks, the TRG will be analyzed for: safety and patients' acceptance of and  
253 adherence to hybrid comprehensive TR.

254

255 **Evaluation of novel model of hybrid comprehensive telerehabilitation in terms of tertiary**  
256 **analyses**

257 Assessment of hybrid comprehensive TR effectiveness.

258 The effectiveness of TR and the comparison of the two arms will be based on the analysis of  
 259 changes (between entry and 9 weeks – intervention period in TRG and observation period in CG) of  
 260 the following parameters: HF functional class according to NYHA, CPET duration, peak oxygen  
 261 consumption (pVO2), % of predicted peak VO2 (pVO2%N), 6-MWT distance, QoL (SF-36) score,  
 262 depression and anxiety assessment.

263

264 Assessment of hybrid comprehensive TR safety.

265 The safety assessment will include the incidence of: adverse events (ischemic symptoms,  
 266 dyspnea – tachypnoe > 20/min, syncope or fainting, passing to a higher NYHA class, putting on  
 267 ≥1.8kg body mass during 1-3 days, symptomatic drop in systolic blood pressure, SVT, AF, nsVT, VT,  
 268 VF, II and III degree atrio-ventricular block, resting HR ≥100/min, left- and/or right-ventricular  
 269 insufficiency, need for urgent hospitalization, death) during exercise training, directly following it (up  
 270 to 1 hour) and adverse events regardless of the training (including data from remote monitoring of  
 271 CIEDs).

272

273 Assessment of the patients' acceptance of hybrid comprehensive TR.

274 The patients' acceptance of TR will be analyzed based on a 12-item questionnaire filled out by  
 275 patients at the end of TR, which will include the assessment of: difficulties in operating the TR set, the  
 276 influence of the TR set of their perceived safety, patients' compliance to the recommendations on  
 277 pharmacotherapy, nutrition and their lifestyle (**Table6**).

278 **Table 6.** Patients' acceptance of hybrid comprehensive telerehabilitation questionnaire.

Questions	Answers (%)
1. Did you control the device by yourself ?	Yes/No
2. Was operating the device:	Very easy / Easy / Difficult / Very difficult
3. Was accurate placing electrodes on your skin difficult?	Yes/No
4. Did you observe any significant skin reaction to electrodes?	Yes/No
5. When using provided equipment to communicate with monitoring centre, was the sound quality satisfactory?	Yes/No
6. Did you find it difficult to coordinate exercise with the instructions from the device?	Yes/Sometimes/No

7. Was transmitting data (ECG, blood pressure) troublesome?	Yes/Sometimes/No
8. Did you ever miss doing a telerehabilitation session because of technical problems? If Yes, how many times?	Yes/No
9. When did you use the telemedicine equipment?	Only during exercise During exercise and when I felt unwell
10. Did TR stimulate you to do exercise?	Yes/Moderately/No
11. Did you feel safer during TR than when you did exercises at home without supervision?	Yes/No
12. Did TR make you increase your everyday activities? Physical exercises Mental Social Professional  Sexual	Yes/No Yes/No Yes/No Yes/No no applicable Yes/No

279 ECG - electrocardiogram; TR - telerehabilitation

280

281 Assessment of the adherence to hybrid comprehensive TR.

282 Adherence during TR will be assessed based on the daily telephone contact with the  
283 monitoring centre, which is required to obtain the necessary permission for the training and  
284 compliance to the exercise training. Adherence is defined as the percentage of patients who carry out  
285 the prescribed exercise training. According to the recommendations, in terms of their adherence, the  
286 patients will be divided into three groups: the first group are adherent patients, i.e. patients who adhere  
287 both to the number of training sessions prescribed and to the duration of the prescribed cycle by at  
288 least 80%; the second category consisted of non-adherent patients, who adhere < 20% to the  
289 prescribed number of training sessions and their duration. The third group correspond to the partially  
290 adherent patients who carry out the prescribed exercise, yet tend to omit some of them or do not carry  
291 them out for the prescribed duration (i.e. who adhere  $\geq 20\%$  and  $< 80\%$ ).

292 **Follow-up**

293 All patients will be followed up for a maximum of 24 months with a maximum of two check-  
294 up visits within the 12 and 24 months following the end of the preliminary 9-week training program in  
295 TRG and the observational period in CG. Each month follow-up will be also conducted via telephone  
296 (conversations with the patient and/or family member) in order to collect data about primary and  
297 secondary endpoints. All patients will be followed-up for a maximum of 24 months after the 9-week  
298 period.

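### Arrhythmia and AV block outside training are to be analysed for safety in the telerehabilitation arm only, although ECG and 24-hour Holter at entry and 9 weeks are done in both arms

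*Protocol*

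**What the plan says.** The Objectives section makes safety a declared tertiary analysis: "evaluation of the safety, effectiveness, quality of life (QoL" and further items are listed together.

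The section Clinical examinations begins "All 850 patients will undergo the following assessments at entry (during 5 days of" and applies one set of tests to both arms at entry and after 9 weeks. The set includes NYHA class, ECG and 24-hour Holter. The section closes with a sentence for one arm only: "after 9 weeks, the TRG will be analyzed for: safety and", followed by acceptance and adherence.

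The section on assessment of TR safety lists the adverse events. They include ischaemic symptoms, syncope, rapid weight gain, SVT, AF, nsVT, VT, VF, second- and third-degree AV block, urgent hospitalization and death. It covers three windows: during training, up to one hour after it, and "adverse events regardless of the training (including data from remote monitoring of" implanted devices. It names neither a control arm nor a comparison. The effectiveness section just before it does: "The effectiveness of TR and the comparison of the two arms will be based on the analysis of" changes between entry and 9 weeks.

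The section Tertiary Outcomes Assessed at 9 weeks specifies between-arm models for functional capacity, quality of life, depression, anxiety and NYHA class. It contains no safety outcome.

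**The concern.** Describing events during a training session in the trained arm alone is proper, because controls have no sessions. Events outside training are different. Patients with LVEF of 40% or less and a recent hospitalization can be expected to have atrial and ventricular arrhythmia and conduction disturbance whether or not they exercise. A TRG-only incidence does not show whether the programme caused these events, prevented them or only detected them.

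Detection differs strongly between the arms. During the programme the TRG has daily contact with the monitoring centre, tele-ECG and, where technically possible, device transmission. For all patients, the only contact described between visits is a monthly telephone call that collects primary and secondary endpoints. An uncompared TRG rate could therefore make the programme look harmful merely because more was seen. It could also be called acceptable with nothing to judge it against. Safety is a stated aim, and for part of the event list randomized control data are already being collected.

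**Working it through.** The protocol gives no adverse-event rate and no precision for safety, so there is no figure to reproduce. The check has two parts.

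**1. Which listed events have a between-arm comparison?**

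| Listed event | Compared by arm? | Where |
|---|---|---|
| Death | Yes, Cox model with site and arm | Secondary Outcomes |
| Hospitalization | Yes, Cox model (all-cause, CV, HF) | Secondary Outcomes |
| Worsening NYHA class | Yes, ordinal logistic model at 9 weeks | Tertiary Outcomes; effectiveness section |
| SVT, AF, nsVT, VT, VF, AV block | No | – |
| Syncope, ischaemic symptoms, pressure drop, rapid weight gain | No | – |

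Deaths and hospitalizations are adjudicated by a committee blinded to allocation (Study design). The Primary Outcome section starts ITT follow-up at randomization, and the secondary analyses use all available follow-up. If the ITT start applies to them too, the training period is included, although rates are quoted at 12 months and no 9-week contrast is stated.

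**2. For the uncovered events, which control data are comparable?**

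- *ECG and 24-hour Holter at entry and 9 weeks:* the same schedule in both arms, so a randomized comparison is possible. The Holter samples one day, so it gives prevalence at the visit and not incidence over 9 weeks.
- *Device (CIED) checks at four and nine weeks:* planned from the "beginning of hybrid TR in TRG and usual care in CG and immediately after the intervention (after 9" weeks), but only for patients with both an implanted device and a remote monitoring device. TRG patients with a CIED receive a transmitter if technically feasible, whereas only some controls have remote monitoring (Control Group). The two subsets arise differently, so comparing them is not a randomized comparison.
- *Symptoms and short-term weight gain:* known in the TRG through daily contact. No equivalent collection is described for controls.

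**Precision of the comparison that is possible.** Target enrolment is 850 at 1:1, so 850/2 = 425 per arm. With a common event rate p, which is assumed, the 95% half-width of the risk difference is 1.96 × √(2p(1−p)/425). For one arm alone, the half-width of the rate is 1.96 × √(p(1−p)/425).

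| Assumed p | Half-width, difference between arms | Half-width, TRG rate alone |
|---|---|---|
| 2% | 1.96 × √(0.0392/425) = 1.9 points | 1.3 points |
| 5% | 1.96 × √(0.0950/425) = 2.9 points | 2.1 points |
| 10% | 1.96 × √(0.1800/425) = 4.0 points | 2.9 points |

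The narrower single-arm interval answers a different question. A TRG rate of 10% with an interval of about 7.1% to 12.9% fits an excess, a deficit or no difference, depending on a control rate that is not reported.

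If 5% of patients had no 9-week recording (the loss rate that the sample size section uses), the half-widths for the difference would grow by 1/√0.95 = 1.026, to about 1.9, 3.0 and 4.1 points.

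**The case against.** The strongest reply is that the restriction rests on one sentence. The safety section itself does not exclude controls, and tables of adverse events by arm are usually set in an SAP. The most serious listed harms, death and hospitalization, are compared by randomized arm with blinded adjudication, and NYHA class is compared at exactly 9 weeks. Safety is a tertiary analysis, and much of the event list could not be compared fairly because controls are observed far less often.

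Most of this stands, and it limits the point. A reader might infer from the TRG-only sentence that excess harm of any kind cannot be told from background disease. The protocol does not support that, since death, hospitalization and NYHA change have randomized comparisons. A reader might also infer that the whole list could be compared at no cost, device checks included. That is not supported either: the device-monitored subsets are selected differently by arm, and symptoms are not collected alike.

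The argument that this is only detail for an SAP does not stand. The protocol does more than stay silent: it assigns the safety analysis to one arm, beside two items that can exist only in that arm, and it names a two-arm comparison for effectiveness but not for safety. An SAP that followed this text would produce an uncontrolled rate.

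**Conclusion.** The point holds for listed events other than death, hospitalization and NYHA change, chiefly arrhythmia and AV block. As written, their safety analysis is confined to the TRG and cannot separate a programme effect from background heart failure or closer monitoring. A randomized comparison of the 9-week ECG and Holter would estimate the difference to within about 1.9 to 4.0 percentage points for rates of 2% to 10%. The plan gives no estimate of it. These figures assume the event rates, about 425 patients per arm and nearly complete 9-week recordings. They do not apply to device-detected events, where the denominators are smaller and not randomized. The primary analysis is unaffected. This is an inexpensive improvement to a declared tertiary aim.

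**What to change.** Amend the sections Clinical examinations and Assessment of hybrid comprehensive TR safety as follows.

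- **Report by randomized arm**, with risk differences and 95% confidence intervals, arrhythmia and AV block on the scheduled 9-week ECG and 24-hour Holter. Present them as prevalence at that visit, take account of the entry recording, and state how many patients in each arm have no 9-week recording, with deaths shown separately.
- **Add a 9-week cut by arm** of the adjudicated deaths and hospitalizations, leaving out the stays that the protocol itself schedules.
- **Keep as descriptive TRG-only data** the events during training and up to one hour after it, events detected only by telemonitoring or device transmission, and symptoms known only through daily contact.
- **Show the device-visit findings descriptively** in each arm, with the reason that the monitored subsets arise differently.

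The cost is a few extra tables from data already planned for collection. The limitation is that a 24-hour Holter captures one day, so the comparison covers part of the event list and should be labelled accordingly.
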